6.3 DATA SHARING PLANS

6.3.1 Human Data Sharing Plan

What data will be shared?

The PI will share human data generated in this research for future research as follows:

- Coded, linked data in an NIH-funded or approved public repository.
- Coded, linked data in BTRIS (automatic for activities in the Clinical Center)
- Identified or coded, linked data with approved outside collaborators under appropriate agreements.

How and where will the data be shared?

Data will be shared through:

- An NIH-funded or approved public repository: clinical trials.gov.
- BTRIS (automatic for activities in the Clinical Center)
- Approved outside collaborators under appropriate individual agreements.
- Publication and/or public presentations.

When will the data be shared?

- Before publication.
- At the time of publication or shortly thereafter.

6.3.2 Genomic Data Sharing Plan

Unlinked genomic data will be deposited in public genomic databases such as dbGaP in compliance with the NIH Genomic Data Sharing Policy.

6.4 **Response Criteria**

For the purposes of this study, patients should be re-evaluated for response every 6 weeks (2 cycles). In addition to a baseline scan, confirmatory scans should also be obtained no less than 4 weeks following initial documentation of objective response.

Response and progression will be assessed by the investigator on the basis of physical examinations, computed tomography (CT) or Magnetic Resonance (MR) scans, and potentially other modalities according to standard of care.

For peritoneal mesothelioma, the international criteria proposed by the revised Response Evaluation Criteria in Solid Tumors (RECIST) guideline (version 1.1)^[17] will be used. Changes in

the largest diameter (unidimensional measurement) of the tumor lesions and the shortest diameter in the case of malignant lymph nodes are used in the RECIST criteria.

For pleural mesothelioma, modified RECIST for MPM (malignant pleural mesothelioma)^[18] should be used as described in section 6.4.2.

6.4.1 Non-Pleural Mesothelioma

6.4.1.1 Disease Parameters

Measurable disease: Measurable lesions are defined as those that can be accurately measured in at least one dimension (longest diameter to be recorded) as:

- By chest x-ray: ≥ 20 mm;
- By CT scan:
 - Scan slice thickness 5 mm or under: ≥ 10 mm
 - Scan slice thickness >5 mm: double the slice thickness
- With calipers on clinical exam: ≥ 10 mm.

Malignant lymph nodes. To be considered pathologically enlarged and measurable, a lymph node must be \geq 15 mm in short axis when assessed by CT scan (CT scan slice thickness recommended to be no greater than 5 mm). At baseline and in follow-up, only the short axis will be measured and followed.

Non-measurable disease. All other lesions (or sites of disease), including small lesions (longest diameter <10 mm or pathological lymph nodes with \geq 10 to <15 mm short axis), are considered non-measurable disease. Bone lesions, leptomeningeal disease, ascites, pleural/pericardial effusions, lymphangitis cutis/pulmonitis, inflammatory breast disease, and abdominal masses (not followed by CT or MRI), are considered as non-measurable.

Note: Cystic lesions that meet the criteria for radiographically defined simple cysts should not be considered as malignant lesions (neither measurable nor non-measurable) since they are, by definition, simple cysts.

'Cystic lesions' thought to represent cystic metastases can be considered as measurable lesions, if they meet the definition of measurability described above. However, if non-cystic lesions are present in the same patient, these are preferred for selection as target lesions.

Target lesions. All measurable lesions up to a maximum of 2 lesions per organ and 5 lesions in total, representative of all involved organs, should be identified as **target lesions** and recorded and measured at baseline. Target lesions should be selected on the basis of their size (lesions with the longest diameter), be representative of all involved organs, but in addition should be those that lend themselves to reproducible repeated measurements. It may be the case that, on occasion, the largest lesion does not lend itself to reproducible measurement in which circumstance the next largest lesion which can be measured reproducibly should be selected. A sum of the diameters (longest for non-nodal lesions, short axis for nodal lesions) for all target lesions will be calculated and reported as the baseline sum diameters. If lymph nodes are to be included in the sum, then only the short axis is added into the sum. The baseline sum diameters will be used as reference to further characterize any objective tumor regression in the measurable dimension of the disease.

Non-target lesions. All other lesions (or sites of disease) including any measurable lesions over and above the 5 target lesions should be identified as **non-target lesions** and should also be recorded at baseline. Measurements of these lesions are not required, but the presence, absence, or in rare cases unequivocal progression of each should be noted throughout follow-up.

6.4.1.2 Methods for Evaluation of Measurable Disease

All measurements should be taken and recorded in metric notation using a ruler or calipers. All baseline evaluations should be performed as closely as possible to the beginning of treatment and never more than 4 weeks before the beginning of the treatment.

The same method of assessment and the same technique should be used to characterize each identified and reported lesion at baseline and during follow-up. Imaging-based evaluation is preferred to evaluation by clinical examination unless the lesion(s) being followed cannot be imaged but are assessable by clinical exam.

Clinical lesions: Clinical lesions will only be considered measurable when they are superficial (e.g., skin nodules and palpable lymph nodes) and ≥ 10 mm diameter as assessed using calipers (e.g., skin nodules). In the case of skin lesions, documentation by color photography, including a ruler to estimate the size of the lesion, is recommended.

Chest x-ray: Lesions on chest x-ray are acceptable as measurable lesions when they are clearly defined and surrounded by aerated lung. However, CT is preferable.

Conventional CT and MRI: This guideline has defined measurability of lesions on CT scan based on the assumption that CT slice thickness is 5 mm or less. If CT scans have slice thickness greater than 5 mm, the minimum size for a measurable lesion should be twice the slice thickness. MRI is also acceptable in certain situations (e.g. for body scans).

Use of MRI remains a complex issue. MRI has excellent contrast, spatial, and temporal resolution; however, there are many image acquisition variables involved in MRI, which greatly impact image quality, lesion conspicuity, and measurement. Furthermore, the availability of MRI is variable globally. As with CT, if an MRI is performed, the technical specifications of the scanning sequences used should be optimized for the evaluation of the type and site of disease. Furthermore, as with CT, the modality used at follow-up should be the same as was used at baseline and the lesions should be measured/assessed on the same pulse sequence. It is beyond the scope of the RECIST guidelines to prescribe specific MRI pulse sequence parameters for all scanners, body parts, and diseases. Ideally, the same type of scanner should be used and the image acquisition protocol should be followed as closely as possible to prior scans. Body scans should be performed with breath-hold scanning techniques, if possible.

PET-CT: At present, the low dose or attenuation correction CT portion of a combined PET-CT is not always of optimal diagnostic CT quality for use with RECIST measurements. However, if the site can document that the CT performed as part of a PET-CT is of identical diagnostic quality to a diagnostic CT (with IV and oral contrast), then the CT portion of the PET-CT can be used for RECIST measurements and can be used interchangeably with conventional CT in accurately measuring cancer lesions over time. Note, however, that the PET portion of the CT introduces additional data, which may bias an investigator if it is not routinely or serially performed.

Ultrasound: Ultrasound is not useful in assessment of lesion size and should not be used as a method of measurement. Ultrasound examinations cannot be reproduced in their entirety for

independent review at a later date and, because they are operator dependent, it cannot be guaranteed that the same technique and measurements will be taken from one assessment to the next. If new lesions are identified by ultrasound in the course of the study, confirmation by CT or MRI is advised. If there is concern about radiation exposure at CT, MRI may be used instead of CT in selected instances.

Endoscopy, Laparoscopy: The utilization of these techniques for objective tumor evaluation is not advised. However, such techniques may be useful to confirm complete pathological response when biopsies are obtained or to determine relapse in trials where recurrence following complete response (CR) or surgical resection is an endpoint.

Tumor markers: Tumor markers alone cannot be used to assess response. If markers are initially above the upper normal limit, they must normalize for a patient to be considered in complete clinical response. Specific guidelines for both CA-125 response (in recurrent ovarian cancer) and PSA response (in recurrent prostate cancer) have been published.^[19-21] In addition, the Gynecologic Cancer Intergroup has developed CA-125 progression criteria which are to be integrated with objective tumor assessment for use in first-line trials in ovarian cancer.^[22]

Cytology, Histology: These techniques can be used to differentiate between partial responses (PR) and complete responses (CR) in rare cases (e.g., residual lesions in tumor types, such as germ cell tumors, where known residual benign tumors can remain).

The cytological confirmation of the neoplastic origin of any effusion that appears or worsens during treatment when the measurable tumor has met criteria for response or stable disease is mandatory to differentiate between response or stable disease (an effusion may be a side effect of the treatment) and progressive disease.

FDG-PET: While FDG-PET response assessments need additional study, it is sometimes reasonable to incorporate the use of FDG-PET scanning to complement CT scanning in assessment of progression (particularly possible 'new' disease). New lesions on the basis of FDG-PET imaging can be identified according to the following algorithm:

- a. Negative FDG-PET at baseline, with a positive FDG-PET at follow-up is a sign of PD based on a new lesion.
- b. No FDG-PET at baseline and a positive FDG-PET at follow-up: If the positive FDG-PET at follow-up corresponds to a new site of disease confirmed by CT, this is PD. If the positive FDG-PET at follow-up is not confirmed as a new site of disease on CT, additional follow-up CT scans are needed to determine if there is truly progression occurring at that site (if so, the date of PD will be the date of the initial abnormal FDG-PET scan). If the positive FDG-PET at follow-up corresponds to a pre-existing site of disease on CT that is not progressing on the basis of the anatomic images, this is not PD.
- c. FDG-PET may be used to upgrade a response to a CR in a manner similar to a biopsy in cases where a residual radiographic abnormality is thought to represent fibrosis or scarring. The use of FDG-PET in this circumstance should be prospectively described in the protocol and supported by disease-specific medical literature for the indication. However, it must be acknowledged that both approaches may lead to false positive CR due to limitations of FDG-PET and biopsy resolution/sensitivity.

Note: A 'positive' FDG-PET scan lesion means one which is FDG avid with an uptake greater than twice that of the surrounding tissue on the attenuation corrected image.

6.4.1.3 RECIST version 1.1 Response Criteria

6.4.1.3.1 Evaluation of Target Lesions

Complete Response (CR): Disappearance of all target lesions. Any pathological lymph nodes (whether target or non-target) must have reduction in short axis to <10 mm.

Partial Response (PR): At least a 30% decrease in the sum of the diameters of target lesions, taking as reference the baseline sum of diameters.

Progressive Disease (PD): At least a 20% increase in the sum of the diameters of target lesions, taking as reference the smallest sum on study (this includes the baseline sum if that is the smallest on study). In addition to the relative increase of 20%, the sum must also demonstrate an absolute increase of at least 5 mm. (Note: the appearance of one or more new lesions is also considered progressions).

Stable Disease (SD): Neither sufficient shrinkage to qualify for PR nor sufficient increase to qualify for PD, taking as reference the smallest sum of diameters while on study.

6.4.1.3.2 Evaluation of Non-Target Lesions

Complete Response (CR): Disappearance of all non-target lesions and normalization of tumor marker level. All lymph nodes must be non-pathological in size (<10 mm short axis).

Note: If tumor markers are initially above the upper normal limit, they must normalize for a patient to be considered in complete clinical response.

Non-CR/Non-PD: Persistence of one or more non-target lesion(s) and/or maintenance of tumor marker level above the normal limits.

Progressive Disease (PD): Appearance of one or more new lesions and/or *unequivocal progression* of existing non-target lesions. *Unequivocal progression* should not normally trump target lesion status. It must be representative of overall disease status change, not a single lesion increase.

Although a clear progression of "non-target" lesions only is exceptional, the opinion of the treating physician should prevail in such circumstances, and the progression status should be confirmed at a later time by the review panel (or Principal Investigator).

6.4.1.3.3 Evaluation of Best Overall Response

The best overall response is the best response recorded from the start of the treatment until disease progression/recurrence (taking as reference for progressive disease the smallest measurements recorded since the treatment started). The patient's best response assignment will depend on the achievement of both measurement and confirmation criteria.

For Patients with Measurable Disease (i.e., Target Disease)

| Target | Non-Target | New | Overall | Best Overall Response when |
|---------|------------|---------|----------|------------------------------|
| Lesions | Lesions | Lesions | Response | Confirmation is Required* |
| CR | CR | No | CR | \geq 4 wks. Confirmation** |

Abbreviated Title: Ph 2 Olaparib in Mesothelioma Version Date: 02/24/20

| Target Lesions | Non-Target Lesions | New Lesions | Overall Response | Best Overall Response when Confirmation is Required* | | |
|--|--|----------------|---------------------|---|--|--|
| CR | Non- CR/Non-PD | No | PR | | | |
| CR | Not evaluated | No | PR | >4 wks. Confirmation** | | |
| PR | Non- CR/Non- PD/not evaluated | No | PR | | | |
| SD | Non- CR/Non- PD/not evaluated | No | SD | Documented at least once ≥ 4 wks. from baseline** | | |
| PD | Any | Yes or No | PD | | | |
| Any | PD*** | Yes or No | PD | no prior SD, PR or CR | | |
| Any | Any | Yes | PD | | | |
| * See RECIST 1.1 manuscript for further details on what is evidence of a new lesion. | | | | | | |
| ** On | Only for non-randomized trials with response as primary endpoint. | | | | | |
| *** In dise | In exceptional circumstances, unequivocal progression in non-target lesions may be accepted as disease progression. | | | | | |
| Note : Pat obj det dise | Patients with a global deterioration of health status requiring discontinuation of treatment without objective evidence of disease progression at that time should be reported as " symptomatic deterioration ." Every effort should be made to document the objective progression even after discontinuation of treatment. | | | | | |

For Patients with Non-Measurable Disease (i.e., Non-Target Disease)

| Non-Target Lesions | New Lesions | Overall Response | |
|--------------------|-------------|-------------------------|--|
| CR | No | CR | |
| Non-CR/non-PD | No | Non-CR/non-PD* | |
| Not all evaluated | No | not evaluated | |
| Unequivocal PD | Yes or No | PD | |
| Any | Yes | PD | |

| Non-Target Lesions | New Lesions | Overall Response |
|---|--|--|
| * 'Non-CR/non-PD' is preferred over an endpoint for assessment of efficac measured is not advised | 'stable disease' for non-target disea by in some trials so to assign this | se since SD is increasingly used as category when no lesions can be |

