- As indicated in section 12.3, all subjects \geq age 18 will be offered the opportunity to complete an NIH advance directives form. This should be done preferably at baseline but can be done at any time during the study as long as the capacity to do so is retained. The completion of the form is strongly recommended, but is not required. 13.
- Performed only if patient removed from study therapy for reason other than progressive disease 14.
- Follow up scans will continue every 6 weeks until disease progression. Scans performed outside the NIH Clinical Center are acceptable. 15.

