3.5.1 Criteria for Removal from Protocol Therapy

- Progressive disease
- Participant requests to be withdrawn from active therapy (see section 3.5.4)
- Requires use of prohibited medication
- Unacceptable Toxicity as defined in section 3.3
- Investigator discretion
- Patient non-compliance
- Positive pregnancy test

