3.5.2 Follow Up

By discontinuing from study treatment, the patient is not withdrawing from the study. Patients should be followed for progression (if discontinuation in the absence of progression) as per the Study Calendar.

Any patient discontinuing investigational product should be seen at 30 days post discontinuation for the evaluations outlined in the Study Calendar at the Treatment discontinuation visit. The patient's tumor status should be assessed clinically and, if appropriate, disease progression should be confirmed by radiological assessment. After discontinuation of study medication, the principal Investigator/Sub-Investigator will perform the best possible observation(s), test(s) and evaluation(s) as well as give appropriate medication and all possible measures for the safety of the patient. In addition, they will record on the eCRF the date of discontinuation, the reasons, manifestation and treatment at the time of discontinuation. Patients will be required to attend the treatment discontinuation visit. The patient should return all study medication.

After discontinuation of the study medication at any point in the study, all ongoing AEs or SAEs must be followed as directed in section 6.2.1). All new AEs and SAEs occurring during the 30 calendar days after the last dose of study medication must be reported (if SAEs, they must be reported to AstraZeneca within 24 hours as described in Section 8.2.1) and followed to resolution as above. Patients should be seen at least 30 days after discontinuing study medication to collect and / or complete AE information. For guidance on reporting adverse events to the manufacturer after the 30-day follow up period see Section 8.2.2.

Any patient who has not yet shown objective radiological disease progression at withdrawal from olaparib should continue to be followed as per RECIST as detailed in Study Calendar.

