4.1 SUPPORTIVE CARE

Unless otherwise indicated in sections 3.3.1 and 3.3.2, toxicities will be managed per current evidence-based practice guidelines in consultation with a medically responsible investigator if available.

4.2 **PROHIBITED MEDICATIONS**

No other anti-cancer therapy (chemotherapy, immunotherapy, hormonal therapy (Hormone replacement therapy (HRT) is acceptable), radiotherapy (unless palliative – see 4.5.2), biological therapy or other novel agent) is to be permitted while the patient is receiving study medication. (Note: Patients may continue the use of bisphosphonates or denosumab for bone disease and corticosteroids for the symptomatic control of brain metastases provided the dose is stable before and during the study and they were started at least 4 weeks prior to beginning study treatment.)

Live virus and live bacterial (including live attenuated) vaccines should not be administered while the patient is receiving study medication and during the 30-day follow up period. An increased

risk of infection by the administration of live virus and bacterial vaccines has been observed with conventional chemotherapy drugs and the effects with olaparib are unknown.

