6.4.5 Objective Response Rate

Objective response rate (ORR) is defined as the proportion of patients with partial response or complete response.

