10.4.6 Planned Interim Analyses

If during the initial 20 patients evaluated, there are 0-1 responses noted, then no further patients will be enrolled as soon as this can be determined. since the upper one-sided 90% confidence interval bound on 1/20 is 18.1%, which is below the approximate response rate of interest. Because accrual is proceeding rapidly on the study and continued enrollment is desirable at this time, up to 25 total patients may be enrolled (5 additional patients) while awaiting the response evaluations among the first 20 patients.

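### The best-overall-response window closes only at progression, so a confirmed response to a later therapy can meet the definition of the primary ORR

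*Combined protocol and SAP*

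**What the plan says.** The window for best overall response is worded identically for non-pleural disease (6.4.1.3.3) and pleural disease (6.4.2.2): "The best overall response is the best response recorded from the start of the treatment until disease progression/recurrence". Section 6.4.5 adds no condition on therapy: "Objective response rate (ORR) is defined as the proportion of patients with partial response or complete response".

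Stopping olaparib does not end tumour assessment. Section 3.5.2 states: "By discontinuing from study treatment, the patient is not withdrawing from the study". It continues: "Any patient who has not yet shown objective radiological disease progression at withdrawal from olaparib should continue to be followed as per RECIST". Footnote 15 of the study calendar (3.4) sets the schedule: "Follow up scans will continue every 6 weeks until disease progression".

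Section 4.2 limits other anti-cancer therapy only for a period; none "is to be permitted while the patient is receiving study medication". Section 3.5.1 lists reasons to leave protocol therapy other than progression, among them toxicity, participant request, investigator discretion and "Requires use of prohibited medication". Starting a new therapy is not among the off-study criteria in 3.5.3.

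The response-evaluable set (10.3.2) requires measurable disease, at least one cycle, at least 50% of doses per cycle and a re-evaluation. Neither it nor the primary analysis (10.4.1, 10.4.2) mentions later therapy. The interim rule in 10.4.6 reads: "If during the initial 20 patients evaluated, there are 0-1 responses noted, then no further patients will be enrolled".

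**The concern.** Each rule is ordinary alone. Together they leave a period, after olaparib and before progression, in which the patient may receive another treatment, is still scanned, and can still record a best response.

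The primary endpoint is the response rate to olaparib, overall and in three mutation groups, and there is no control arm in which the same contamination would appear. A response borrowed from a later therapy can only raise the estimate. The interim rule turns on a single response, and 10.2 and 10.4.2 use the results to decide whether more patients are enrolled by amendment.

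**Working it through.** **1. Does the text close the window anywhere?** The places where it could do so are 6.4.1.3.3, 6.4.2.2, 6.4.5, 10.3.2, 10.4.1, 10.4.2 and 10.4.6, and none does. The off-study list in 3.5.3 does not end assessment at a new therapy either.

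**2. A patient traced through the rules (illustrative).** The patient takes three full 21-day cycles (9 weeks), stops at week 9 with stable disease, and starts another drug at week 11. Scans at weeks 18 and 24 show PR. The scans are 6 weeks apart, so the confirmation requirement of at least 4 weeks is met. Dosing was adequate in every cycle, so the patient is evaluable under 10.3.2. No progression came before the PR, so it lies inside the window and counts under 6.4.5.

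**3. The plan's own figure.** The one-sided 90% exact (Clopper-Pearson) upper bound for x responses in n is the 0.90 quantile of Beta(x+1, n−x).
- 1/20: Beta(2, 19) gives 0.1810. This reproduces the stated 18.1%, so the rule stops.
- 2/20: Beta(3, 18) gives 0.2448, or 24.5%. This is above the 20% rate of interest, so the rule continues.

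**4. Effect of one borrowed response on the estimate.**
- n=20: 1/20 = 5 points.
- n=30: 1/30 = 3.3 points.
- Group 1, expected at 10-12% of 30 (3 to 3.6, so 3 or 4 patients): 1/4 to 1/3, or 25 to 33 points, but only if that patient belongs to Group 1.

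**5. Effect on the interim stop (all inputs assumed).** Let X be true olaparib responses among 20, with true ORR 5%. Let B be borrowed responses, Binomial(m, r), from m patients who leave without progression and start a drug with response rate r. Every borrowed response is assumed to be seen before the interim decision.
- P(X=0) = 0.95^20 = 0.358.
- P(X=1) = 20 × 0.05 × 0.95^19 = 0.377.
- With no borrowing, P(stop) = 0.358 + 0.377 = 0.736, or 74%.
- With borrowing, P(stop) = P(X=0) × P(B≤1) + P(X=1) × P(B=0).

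| m | r | P(B=0) | P(B≤1) | P(stop) |
|---|---|---|---|---|
| 2 | 10% | 0.810 | 0.990 | 66% |
| 3 | 20% | 0.512 | 0.896 | 51% |
| 4 | 30% | 0.240 | 0.652 | 32% |

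This treats X and B as additive. If no patient may be counted twice, the results are 66%, 52% and 33%.

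Given exactly one borrowed response, a stop needs X=0, which has probability 36%. That figure is conditional. It is not the expected effect of the wording.

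**The case against.** **The dosing rules remove many of these patients.** Section 3.2 makes anyone who misses more than half the doses in a cycle inevaluable and removes them from the study, and 10.3.2 repeats the dose condition. Toxicity is often handled by interruptions of up to 4 weeks (3.3), longer than a 21-day cycle. Read literally, many toxicity stops leave the ORR set. This stands, and it narrows the route. It does not close it, because a patient who stops at or near a cycle boundary after adequate dosing remains evaluable.

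**The endpoint is response to olaparib.** Section 10.1.1 says so, and a sensible investigator might not count a response that first appears on another drug. That shows the intent, but the operational definitions in 6.4 do not carry it out. Response is investigator-assessed in an open-label study, so the matter would be left to unwritten judgement on the primary endpoint.

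**The cited response guidelines may limit the window.** Sections 6.4 and 6.4.1.3.3 refer to them. They are not part of these documents, and the protocol writes out its own window, so they cannot be relied on here.

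**Radiotherapy to a target lesion is already limited.** During treatment this largely holds: 4.5.2 describes palliative radiotherapy to bony metastases, and 6.4.1.1 classes bone lesions as non-measurable. It does not cover the period after olaparib.

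**Closing the window can lose a real response.** An olaparib PR may have its confirmatory scan after new therapy begins. This stands, and the fix needs a rule for it.

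A reader might also infer that the study never records later therapy. The documents do not support that: the calendar table is damaged in the available text, a concomitant-medication row exists whose span cannot be read, and the case report form is not shown.

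**Conclusion.** The point holds as a defect in the endpoint definition. Applied as written, the window admits a confirmed response to a later therapy into the primary ORR for an evaluable patient who left olaparib without progression. The direction is certain, since the estimate can only rise. The size is one response at a time: 3.3 points at n=30, and enough to turn 1/20 into 2/20 at the interim.

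The frequency is not given in the documents and is probably low. The fall in stopping probability from 74% to between about 66% and 32% rests wholly on the assumed inputs, including that borrowed responses appear before the interim decision.

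Two stronger readings are tempting. One is that the wording halves the chance of stopping, from 74% to 36%; that holds only once exactly one borrowed response has occurred. The other is that every patient who stops for toxicity and later responds would be counted, or that the trial's ORR is in fact inflated. The evaluability rules contradict the first part, and nothing in the documents shows that any such response occurred.

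**What to change.** - In 6.4.1.3.3 and 6.4.2.2, define the window as running from start of treatment until progression or the start of any new anti-cancer therapy, whichever is first. Count surgery or radiotherapy to a target lesion as new therapy for this purpose.
- Refer to this window in 6.4.5 and 10.4.6, so that the final ORR and the interim count use the same rule.
- Record the start date of new therapy at the follow-up scans already scheduled.
- State in advance how to count a PR or CR first documented before new therapy but with its confirmatory scan after it. One option is to treat it as unconfirmed in the primary ORR and list it separately.

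The cost is one clause in two sections, two cross-references, one date field and one counting rule. No visit, scan, sample size or treatment rule changes. The downside is that ORR may be slightly less favourable and an occasional genuine response may count as unconfirmed. A sensitivity analysis that censors PFS at new therapy is optional and is not needed for this fix.
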